6.4 Study Treatment Compliance

The prescribed dosage, timing, and mode of administration may not be changed, except as defined in Section [6.6](#).

Only subjects enrolled in the study may receive study treatment and only authorized study center staff may administer the study treatment to the subject.

The Investigator or qualified designee will record each dose by noting the time and number of total sprays administered successfully in a dosing log.

6.4.1 Treatment Strategy for Emergencies

The clinical study center is a large clinical pharmacology Inpatient Unit that has 24-hour staffing and security coverage 7 days a week and is located within 5 miles of 3 local hospitals, one of which is a trauma center. Highly trained Paramedic/Emergency Medical Technicians (EMT) are available in the study center on a 24-hour basis and are trained to deal specifically with life-threatening AEs and medical emergencies. All EMTs are Advance Cardiovascular Life Support certified, and all study center staff are Cardiopulmonary Resuscitation certified. All equipment necessary for resuscitative care is available in the study center. The study center is equipped with 24/7 video surveillance/controlled access throughout the facility, strategically located panic buttons, 48-channel cardiac telemetry and continuous pulse oximetry and 2 emergency crash carts.

6.4.2 Warnings and Precautions

As this is the first administration of OP0201 to healthy human volunteers, all effects cannot be reliably predicted. The preclinical data suggest an acceptable safety profile. In addition, the active pharmaceutical ingredients in the study treatment are endogenous to humans. Facilities and staff for resuscitation and the treatment of other medical emergencies will be provided.

6.5 Concomitant Therapy

Any medication or vaccine (including over-the-counter or prescription medicines, vitamins, and/or herbal supplements) that the subject is receiving at the time of enrollment (within 7 days before the time of enrollment) or receives during the study must be recorded on the electronic case report form (eCRF) along with:

- Reason for use.
- Dates of administration including start and end dates.
- Dosage information including dose and frequency.

The Medical Monitor should be contacted if there are any questions regarding concomitant or prior therapy.

Subjects must abstain from taking prescription or nonprescription drugs (including vitamins and dietary or herbal supplements) within 7 days or 5 half-lives (whichever is longer) before the start of study treatment until completion of the study exit visit (Day 21). In the case of medications (either topically or systemically) for a condition related to ear or nose, subjects must abstain from taking these within 12 weeks before the start of study treatment, or 2 weeks in the case of medications with known vasoconstrictive properties (eg, local anesthetics, decongestants), or 6 weeks in the case of medications with known anti-cholinergic side effects (eg, antihistamines, antiemetics, muscle relaxants, antidepressants). An exception is that women of childbearing potential (WOCBP) may take protocol defined acceptable oral contraceptives.

Acetaminophen, at doses of \leq 3 grams/day, is permitted for use any time during the study. Other concomitant medication may be considered on a case-by-case basis by the Investigator in consultation with the Medical Monitor (if required).

6.6 Dose Modification

Dose modifications are not planned in this study.

6.7 Treatment After the End of the Study

The Sponsor will not provide any additional care to subjects after they leave the study.

7.0 DISCONTINUATION OF STUDY TREATMENT AND SUBJECT DISCONTINUATION/WITHDRAWAL

If a clinically significant finding is identified, the Investigator or qualified designee will determine if the subject should continue with the study treatment and if any change in subject management is needed, and/or if they should remain in the study. Any new clinically relevant finding should be reported as an AE.

7.1 Discontinuation of Study Treatment

Subjects should not receive further study treatment if one or more of the following criteria are met. It is not necessary to exit the participant from the study as long as they do not receive further study treatment. The Investigator may use their discretion in deciding whether to discontinue the participant from the study. If the subject is discontinued from the study early, see SoA (Section 1.3) for data to be collected at the time of study discontinuation. The reason that the study treatment is stopped should be documented on the appropriate eCRF.

7.2 Subject Discontinuation/Withdrawal from the Study

Randomized subjects who meet any of the following criteria should not receive further study treatment and should be exited from the study. See SoA (Section 1.3) for data to be collected at the time of study exit.

- Investigator or Sponsor (or its designee) decides to discontinue subjects from the study for safety, behavioral, compliance, or administrative reasons.
- Investigator or Sponsor (or its designee) decides to discontinue subjects from the study who are inadvertently enrolled into the study despite significant deviation from protocol-specified inclusion/exclusion criteria.
- Subject indicates that they no longer want to participate in the study. If the subject withdraws consent for disclosure of future information, the Sponsor may retain and continue to use any data collected before such a withdrawal of consent. If a subject withdraws from the study, he/she may request destruction of any samples taken and not tested, and the Investigator must document this in the study center study records.

Notification of early subject withdrawal from the study and the reason for discontinuation will be clearly documented and noted in the eCRF. If the subject exits the study prior to the Day 21 study exit visit, all of the Day 21 final measurements should be performed and recorded on the appropriate eCRF.

Subjects who are discontinued from the study may be replaced based on the Sponsor's discretion.

7.3 Lost to Follow-up

A subject will be considered lost to follow-up if he or she repeatedly fails to return for scheduled visits and is unable to be contacted by the study center.

The following actions must be taken if a subject fails to return to the clinic for a required study visit:

- The study center must attempt to contact the subject and reschedule the missed visit as soon as possible and counsel the subject on the importance of maintaining the assigned visit schedule and ascertain whether or not the subject wishes to and/or should continue in the study.
- Before a subject is deemed lost to follow-up, the Investigator or designee must make every effort to regain contact with the subject (where possible, 3 telephone calls and, if necessary, a certified letter to the subject's last known mailing address or local equivalent methods). These contact attempts should be documented in the subject's medical record.
- Should the subject continue to be unreachable, he/she will be considered to have withdrawn from the study.

8.0 STUDY ASSESSMENTS AND PROCEDURES

This section provides a high-level summary of the study assessments to be performed. For details as to when these assessments are performed see the SoA (Section 1.3)

- Study procedures and their timing are summarized in Section 1.3.
- Protocol waivers or exemptions are not allowed.
- Immediate safety concerns should be discussed with the Sponsor designee immediately upon occurrence or awareness to determine if the participant should continue or discontinue study treatment.
- Adherence to the study design requirements, including those specified in the SoA, is essential and required for study conduct.
- All screening evaluations must be completed and reviewed to confirm that potential participants meet all eligibility criteria. The Investigator will maintain a screening log to record details of all participants screened and to confirm eligibility or record reasons for screening failure, as applicable.
- Procedures conducted as part of the subjects' routine clinical management (eg, blood count) and obtained before signing of the ICF may be utilized for screening or baseline purposes provided the procedures met the protocol-specified criteria and were performed within the time frame defined in the SoA.
- The maximum amount of blood collected from each subject over the duration of the study, including any extra assessments that may be required, will not exceed 450 mL. Repeat or unscheduled samples may be taken for safety reasons or for technical issues with the samples.

8.1 Efficacy Assessments

This is a Phase 1 safety study, there are no efficacy assessments.

8.2 Safety Assessments

Planned time points for all safety assessments are provided in the SoA (Section 1.3).

8.2.1 Physical Examinations

- A complete physical examination will be performed to assess any physical abnormalities and will include at a minimum, assessments of the following body systems: general appearance, overall status of the skin, head, neck, trunk, eyes, heart and lungs (eg, breathing sounds), abdomen, extremities, lymph nodes.
- Height and weight will also be measured and recorded at the Screening visit.
- Investigators should pay special attention to clinical signs related to previous serious illnesses.

8.2.2 Vital Signs

Vital signs are to be taken before blood collection for laboratory tests.

- Systolic and diastolic blood pressure (mmHg): to be assessed after a participant has been at rest (seated) for at least 5 minutes in a quiet setting without distractions (eg, television, cell phones) with a completely automated device. Manual techniques will be used only if an automated device is not available. A total of 3 consecutive blood pressure readings will be recorded at intervals of at least 1 minute. The average of the 3 blood pressure readings will be recorded on the eCRF.
- Pulse rate (beats/minute): to be assessed after a subject has been at rest (seated) for at least 5 minutes in a quiet setting without distractions (eg, television, cell phones) with a completely automated device. Manual techniques will be used only if an automated device is not available. A total of 1 pulse reading should be recorded.
- Respiration rate (per minute) will be measured by counting at least 30 seconds and multiplying accordingly. Respiration rate may be taken concurrently with all ECGs.
- Oral temperature (as Fahrenheit degrees) will be assessed and recorded.

8.2.3 Electrocardiograms

- A single 12-lead ECG will be performed at the Screening visit to ensure that a study subject does not have, in the Investigator's clinical judgement, a clinically significant condition or a condition that may pose an unacceptable safety risk for participation in the study.
- For subjects in Cohort A, a single 12-lead ECG will be collected on Day 1 prior to the first dose and on the study exit visit (Day 21).
- For subjects in Cohort B, triplicate 12-lead ECGs will be collected at subsequent visits as outlined in the SoA (see Section 1.3) using an ECG machine that automatically calculates the heart rate and measures PR, QRS, QT, and QTc intervals.
- In cases where ECG and PK sampling overlap, ECGs should be collected first, to ensure that PK samples are collected at the scheduled time point.
- At each time point at which triplicate ECGs are required, 3 individual ECG tracings should be obtained as closely as possible in succession, but no more than 2 minutes apart. The full set of triplicates should be completed in less than 4 minutes.
- ECGs will be assessed by a central ECG reading center. A cardiologist will review screening, pre- and post-treatment ECGs and discuss any abnormal findings with the Investigator, as appropriate.

8.2.4 Clinical Safety Laboratory Assessments

- See [Appendix 3](#) for the list of clinical laboratory tests to be performed and to the SoA for the timing and frequency.
- The Investigator must review the laboratory report, document this review, and record any clinically relevant changes occurring during the study in the AE section of the eCRF. The laboratory reports must be filed with the source documents. Clinically significant abnormal laboratory findings are those that are not associated with the underlying disease, unless judged by the Investigator to be more severe than expected for the subject's condition.
- All laboratory tests with values considered clinically significantly abnormal during participation in the study should be repeated until the values return to normal or baseline or are no longer considered clinically significant by the Investigator or Medical Monitor.
 - If such values do not return to normal/baseline within a period of time judged reasonable by the Investigator, the etiology should be identified, and the Sponsor notified.
 - All protocol-required laboratory assessments, as defined in [Appendix 3](#), must be conducted in accordance with the Laboratory Manual and the SoA.
 - If laboratory values from non-protocol-specified laboratory assessments performed at the institution's local laboratory require a change in subject management or are considered clinically significant by the Investigator (eg, SAE or AE or dose modification), then the results must be recorded in the eCRF.

8.2.5 Otoscopy

Otoscopy will be performed to assess the appearance of the tympanic membrane (normal or abnormal). If abnormal, then it will be rated for the following variables:

- Contour (retracted, full, bulging, perforated).
- Color (partly red or completely red).
- Color of fluid behind the tympanic membrane (yellow, dark red, bright red, green, or clear).
- Translucency (semi-opaque, opaque).

8.2.6 Tympanometry

Tympanometry will be performed to assess tympanic membrane mobility, ET function and ME function by measuring the amount of sound energy reflected back when a small probe is placed in the ear canal ([Rosenfeld et al, 2016](#)). The output of the right ear and left ear tympanometry will be a tympanogram tracing classified as Type A (normal), Type B (abnormal) or Type C (abnormal) ([Jerger, 1970](#)).

8.2.7 Nasal and Epipharynx Endoscopy

Nasal and epipharynx endoscopy will be assessed for normal or abnormal appearance. Under abnormal, the following criteria should be assessed:

- Swelling
- Redness
- Bleeding
- Rhinorrheoea (nose only)
- Other

At the Screening visit, as a part of the nasal endoscopy, the length of the nasal cavity (in mm) will be recorded separately for the left and right side. The length of the nasal cavity is defined as the distance from the tip of the nose to the entry point of the ET.

For all other scheduled assessments, the nasal and epipharynx endoscopy assessment should be done prior to the first dose of the day.

8.2.8 Olfactory Test

An olfactory test, UPSIT, will be performed at the Screening (Day -28 to Day -1) visit to ensure that a subject does not have a clinically significant condition or a condition that may pose an unacceptable safety risk for participation in the study. At the Day 8 and Day 14 visits, an olfactory test will be performed to assess for abnormal olfactory function after the dosing period. If abnormal findings are present at the Day 14 visit, then an additional olfactory test will be performed at the Day 21 study exit visit.

The UPSIT test consists of 4 booklets containing 10 odorants apiece, 1 odorant per page. The stimuli are embedded in 1 μ m to 50 μ m diameter microencapsulated crystals located on brown strips at the bottom of each page. Above each odorant strip is a multiple-choice question with 4 alternative responses for each item. For example, 1 of the items reads, “This odor smells most like: a) chocolate; b) banana; c) onion; or d) fruit punch.” The response “banana” is correct in this case. The subject is required to answer 1 of the 4 alternatives, even if no smell is perceived (ie, the test is forced-choice). This helps to encourage the subject to sample each odorant and provides a basis for the detection of malingering. To ensure uniformity in test administration, the test booklets should be administered in chronologic order, eg, booklet 1, booklet 2, etc. (Doty 1984). A total UPSIT score of <35 is abnormal for females and a total score <34 is abnormal for males. In this study we intend to determine if there is any change from ‘normal’ (at baseline) to ‘abnormal’ post-treatment. If such a change occurs it will be captured as an AE. The severity of the AE will be assessed as per the resulting ‘olfactory diagnosis’ in the following table:

Test Score	Olfactory Diagnosis
00-05	Probable Malingering
06-18	Total Anosmia
19-25	Severe Microsmia
26-29	Moderate Microsmia (males)
26-30	Moderate Microsmia (females)
30-33	Mild Microsmia (males)
31-34	Mild Microsmia (females)
34-40	Normosmia (males)
35-40	Normosmia (females)

8.2.9 Audiology Pure Tone Hearing Test

An audiology pure tone hearing test will be performed at the Screening (Day -28 to Day -1) visit to ensure that a subject does not have clinically significant abnormal hearing. Average pure tone hearing loss at 4 frequencies (500, 1000, 2000 and 4000 Hz) ranges from normal hearing to moderate hearing loss (0-55 dB) will be tested. The 50th percentile is about 25 dB hearing level (HL). Average pure tone audiometry will be performed as per the audiology testing template in [Appendix 10](#). The hearing test should be performed in a quiet environment, preferably a separate closed or sound-proofed area set aside specifically for that purpose. Comprehensive audiologic evaluation is recommended for anyone who fails the pure tone hearing test. Audiologic assessment includes evaluating air-conduction and bone-conduction thresholds for pure tones, speech detection or speech recognition thresholds, and measurements of speech understanding, if possible ([Rosenfeld et al, 2004](#)).

8.3 Adverse Events

The definitions of an AE or SAE can be found in [Appendix 4](#).

Adverse events will be reported by the subject.

The Investigator and any designees are responsible for detecting, documenting, and recording events that meet the definition of an AE or SAE and remain responsible for following up AEs that are serious, considered related to the study treatment or study procedures, or that caused the subject to discontinue the study treatment or the study (see Section [4.6](#) and [7.0](#)).

8.3.1 Time Period and Frequency for Collecting AE and SAE Information

All SAEs will be collected from the time first exposure to the study treatment until the study exit.

All AEs will be collected from the time first exposure to the study treatment until the study exit.

Medical occurrences that begin before the start of study treatment but after obtaining informed consent will be recorded as pre-treatment-emergent AEs in the AE section of the eCRF.

All SAEs will be recorded and reported to the Sponsor or designee within 24 hours, as indicated in [Appendix 4](#). The Investigator will submit any updated SAE data to the Sponsor within 24 hours of it being available.

Investigators are not obligated to actively seek AE or SAE after conclusion of the study participation. However, if the Investigator learns of any SAE, including a death, at any time after a subject has been discharged from the study, and he/she considers the event to be reasonably related to the study treatment or study participation, the Investigator must promptly notify the Sponsor.

The method of recording, evaluating, and assessing causality of AE and SAE and the procedures for completing and transmitting SAE reports are provided in [Appendix 4](#).

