4.6 Study Stopping Criteria

4.6.1 Stopping Criteria for Individual Subjects

Study treatment for any individual subject will be stopped if the subject experiences a serious adverse event (SAE) or a clinically significant possibly drug-related related AE, which in the opinion of the study physician, Principal Investigator, or Sponsor's medical representative, warrants discontinuation of the study for that subject's wellbeing. See Section [7.1](#) for general discontinuation procedures.

Any female subject who becomes pregnant while participating in the study will be withdrawn from the study.

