The study treatment will be administered every 7 hours: a morning dose at 9:00 am, an afternoon dose at 16:00 pm and an evening dose at 23:00 pm. The Investigator or qualified designee will record each dose by noting the time and number of total sprays administered successfully in a dosing log.

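### A treated subject withdrawn from the study has no guaranteed period of new-AE collection after the last dose, against 7 to 12 days for completers

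*Protocol*

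**What the plan says.** **Collection window.** Protocol 8.3.1: "All AEs will be collected from the time first exposure to the study treatment until the study exit". The sentence for SAEs is parallel: "All SAEs will be collected from the time first exposure to the study treatment until the study exit". It adds that "Investigators are not obligated to actively seek AE or SAE after conclusion of the study participation". One duty survives exit: "if the Investigator learns of any SAE, including a death, at any time after a subject has been discharged from the study" and thinks it reasonably related, the Sponsor must be told promptly.

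**Completers.** Dosing runs for 14 days, with the third daily dose at 23:00 (Protocol 6.1). Study exit is Day 21 with a +5 day window (Protocol 4.1).

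**Stopping treatment only.** Protocol 7.1: "It is not necessary to exit the participant from the study as long as they do not receive further study treatment". Whether the subject also leaves the study is left to the Investigator. The section announces a list of criteria, but none appears in the text.

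**Leaving the study.** Protocol 7.2: subjects meeting its criteria "should not receive further study treatment and should be exited from the study". One criterion is a decision by the Investigator or Sponsor to discontinue the subject from the study, with safety among the possible reasons. The Day 21 measurements are then done at exit.

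**The EaT visit.** The Schedule of Activities (Protocol 1.3) places it under Study Exit. Footnote b says whom it is for, but gives no day, window or interval from the last dose. SAP 7.6 pools its results with Study Exit, and SAP Appendix 1 lists it under that heading.

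**Analysis.** SAP 17.1 tabulates TEAEs as numbers and percentages of subjects. SAP 8.2 does not impute missing safety data, apart from items such as dates, AE severity and relationship.

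**The concern.** AE collection is tied to study exit, and for a withdrawn subject exit can come as soon as dosing stops. A subject removed because the product was poorly tolerated could then have the shortest observation in the trial. The incidence tables would count that subject as fully as one observed to Day 21, so the unobserved days are in effect treated as event-free.

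This matters because safety and tolerability is the primary objective. Protocol 6.4.2 describes the study as the first administration to healthy volunteers, with effects that cannot all be predicted. The study stopping rules in 4.6.3 turn on one or two subjects, and the escalation decision rests on Cohort A safety data.

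The route by which a subject leaves decides the follow-up, and the text on that route is not clean. Section 4.6.1 is about stopping treatment, yet describes an AE that "warrants discontinuation of the study for that subject's wellbeing".

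**Working it through.** The documents state no hypothesis, alpha or power, so the check is calendar arithmetic.

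**1. Reproduce the plan's own figure.** Screening covers Days -28 to -1, which is 28 days. The latest exit is Day 21 + 5 = Day 26. 28 + 26 = 54 days, matching the maximum participation stated in Protocol 4.1.

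**2. Completers.** Formula: exit day minus day of last dose (Day 14).
- Earliest: 21 - 14 = 7 days.
- Latest: 26 - 14 = 12 days.
- By the clock, from 23:00 on Day 14: 6.4 days to an 08:00 visit on Day 21, and 11.8 days to a 17:00 visit on Day 26. The visit hours are an assumption.

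**3. Treated subjects who leave the study or stop treatment early.** Let d be the day of the last dose.

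| Route | New-AE collection after last dose | Example |
|---|---|---|
| Withdrawn during dosing, EaT visit on day d | d - d = 0 days | About 0 for any d; the lowest value the text allows |
| Withdrawn after finishing dosing, exit on Days 15 to 20 | exit day - 14 | 1 to 6 days |
| Stops treatment, stays in the study (7.1) | (21 - d) to (26 - d) | d = 4: 17 to 22 days; d = 8: 13 to 18 days |

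Two subjects who stop on Day 8 can therefore have 13 to 18 days of new-AE collection or about 0, depending on whether they are also taken out of the study.

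**4. Weight of one missed event.** Each active group has 12 subjects: 1/12 = 8.3 percentage points. The pooled placebo group has 3 + 3 = 6: 1/6 = 16.7 points. Both assume that the denominator is all treated subjects in the group.

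**5. Number affected.** The documents give no early-exit rate. Taking 0 to 3 early exits among 30 as an assumed range gives 0/30 = 0% to 3/30 = 10%.

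**The case against.** A reader might infer several stronger points that the documents do not support.

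- **That everyone who stops early loses follow-up.** Section 7.1 lets a subject stop treatment and stay. As the table shows, such a subject can be followed for longer than a completer.
- **That about 0 days is what the plan prescribes.** No passage says that exit falls on the day of the last dose. Zero is the minimum allowed by an EaT visit with no timing.
- **That 4.6.1, 7.1 and 7.2 flatly contradict one another on an AE-driven stop.** Section 4.6.1 sends the reader to 7.1 for procedures. Section 7.2 requires exit once someone has decided to discontinue the subject from the study, which fits the discretion in 7.1. What remains is loose wording in 4.6.1 and a missing list in 7.1.
- **That nothing is followed after exit.** Protocol 8.3 keeps the Investigator responsible for AEs that are serious, related, or led to stopping treatment or leaving the study. Protocol 8.3.3 requires reported AEs to be followed until they settle, are explained or the subject is lost. Related SAEs learned of later must be reported.

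The safety analysis is also descriptive, with no between-group tests unless otherwise specified (SAP 17). Withdrawal dates and reasons are listed by subject (SAP 10), so a short observation would be visible. The amendment rationale justifies the shorter follow-up by the drug being short acting, with no known or projected long-term adverse events. In a 14-day residential study, early exits may be few.

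These points limit the size of the problem but do not remove it. None provides for active collection of new-onset events after an early exit: non-serious AEs would not be collected, and SAEs would depend on someone reporting them and on a judgement that they were related. Listing a withdrawal date shows the gap but cannot fill it.

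**Conclusion.** The point holds for treated subjects withdrawn from the study, under 7.2 or by discretion under 7.1. For them the plan guarantees no post-dose period of new-AE collection: it may be as little as about 0 days, against 7 to 12 for completers. Withdrawals after dosing but before Day 21 have 1 to 6 days. It does not apply to subjects who stop treatment and remain in the study, or to AEs already open at exit.

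The conclusion rests on reading the EaT visit as study exit, which the Schedule of Activities and the SAP both support, and on the visit taking place when the subject leaves, which is a natural reading but not stated. The effect on any one AE term is 8.3 points per missed event in an active group. The total effect cannot be computed without an early-exit rate and may be nil. This is a modest, inexpensive gap in the primary safety data and does not undermine the design.

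**What to change.** **Protocol 8.3.1, 7.2 and Schedule of Activities footnote b (with its copy in SAP 4.2).** State that for any treated subject withdrawn from the study who has not withdrawn consent to contact, new AEs, SAEs and concomitant medications are collected, by telephone or visit, through the same interval after the last dose that completers have: 7 days (+5). This is in addition to the EaT assessments at discontinuation. State also that subjects who stop treatment but remain under 7.1 continue to Day 21 (+5) as now, so that the change shortens nobody's follow-up.

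**Protocol 4.6.1, 7.1 and 7.2.** Reconcile the wording on whether an AE-driven treatment stop ends study participation, and either supply the criteria that 7.1 announces or remove the reference to them. Which rule applies is for the sponsor and the investigator to decide; the request is only that the sections agree.

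**Cost.** A small amendment and about one extra contact per early leaver. Some may decline, so the gap would be narrowed rather than closed. Dosing and the stopping rules are unchanged.
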